However, currently, the routine use of prophylactic drains after colorectal surgery is still widespread (15). As part of our last EuroSurg study, IMAGINE (16), centres filled out a survey regarding their adherence to ERAS guidelines. Preliminary data has shown that 35% of participating centres routinely leave drains after colorectal surgery for most of their patients.

Reasons to justify drainage after colorectal surgery include: prevention of complicated intra-abdominal collections; early detection of haemorrhage, anastomotic leakage, or other complications, and reduction of the incidence of anastomotic leak and pelvic sepsis (17,18). On the other hand, the routine placement of prophylactic drains is also associated with adverse events. Drains have been shown to be associated with an increased production of serous fluid, which could lead to wound infections, promote adhesions and could even result in a higher risk of anastomotic leak (19,20). In addition, they could cause irritation and offer an inward track for contamination.

It is common opinion that early detection of intra-abdominal collections might prevent additional surgical or percutaneous procedures necessary during the postoperative period (21). However, there is no consensus on which type of drain should be used and for how long it should be left in situ.

The aim of this international multi-centre cohort study is to define the incidence of drain placement after colorectal surgery and to describe drain management practices.

Methods

1. Definition for intra-abdominal collections

Postoperative collection altering the normal postoperative course management and requiring antibiotics or radiological/endoscopic/surgical intervention.

2. Summary

“Mini-teams” of up to three collaborators (medical students and/or doctors) per data collection period will prospectively collect data over a continuous 14-day period at each participating centre. This will be on consecutive patients undergoing elective or emergency colorectal surgery, with follow-up to 30 postoperative days. All mini-teams should be supervised by one surgical consultant of reference per centre. Each participating centre will be required to fill out a survey regarding their local drain management practices.

3. Study Aims

- **Primary Aim:** To audit compliance to Enhanced Recovery After Surgery (ERAS) guidelines on avoiding routine placement of prophylactic drains in colorectal surgery.
- **Secondary Aims:**

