 - To assess whether placement of a postoperative drain is associated with earlier detection of collections and anastomotic leak.
 - To examine when drains can be safely removed.
 - To explore the clinical decision-making process for drain placement after colorectal surgery.
 - To characterise the incidence of complicated postoperative collections and their clinical management in colorectal surgery in an international cohort.

4. Project Timeline

Data collection will take place between 3rd February 2020 and 26th April 2020 during the following four predefined 14-day data collection periods.

- **Period 1:** 08:00 AM 3 Feb 2020 to 08:00 AM 17 Feb 2020 (+ 30 Day Follow-up)
- **Period 2:** 08:00 AM 24 Feb 2020 to 08:00 AM 09 Mar 2020 (+ 30 Day Follow-up)
- **Period 3:** 08:00 AM 16 Mar 2020 to 08:00 AM 30 Mar 2020 (+ 30 Day Follow-up)
- **Period 4:** 08:00 AM 13 Apr 2020 to 08:00 AM 27 Apr 2020 (+ 30 Day Follow-up)

An extra period may be opened at the discretion of the steering committee to allow for the participation of centres that encountered difficulties in obtaining the necessary ethical approvals:

- **Period 5:** 08:00 AM 27 Apr 2020 to 08:00 AM 11 May 2020 (+ 30 Day Follow-up)

At each hospital, one mini-team per period will collect data on eligible patients admitted over a 14-day period. Data on 30-day outcomes after the day of surgery will also be collected. The deadline for uploading collected data onto REDCap is 30th June 2020.

Patients should be included if their operation started (defined as 'knife-to-skin' time) within the time period during the data collection periods as specified above.

One mini-team of up to three collaborators can take part in each 14-day period. Multiple mini-teams can participate at each centre, but no more than one team per period at the same centre. To be listed as PubMed-citable collaborators, centres are required to participate in at least one data collection period.

5. Centres

- COMPASS is open to any hospital in the member countries of the European Society of Coloproctology (ESCP), the Royal Australasian College of Surgeons (RACS) and South African centres, which routinely perform elective or emergency colorectal surgery. Participation of centres from other countries will be considered on a case-by-case basis.

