▲ If an in-hospital patient recovering from another primary procedure NOT previously included undergoes emergency surgery, this **MUST** be included in the study as emergency case. ▲

i.e. Patient A is recovering from an AAA repair and undergoes large bowel resection due to bowel ischaemia one day later the previous surgery. He was correctly not included after the AAA repair, as that is a primarily vascular procedure and it did not involve any large bowel resection, but should be included after the bowel resection.

- ▲ You should collect data on consecutive elective patients operated at your hospital during the data collection period. **All eligible patients** must be included. Strategies to identify consecutive patients could include: ▲
- Daily review of elective theatre lists.
 - Daily review of handover sheets and ward lists.
 - Daily review of theatre logbooks
 - Daily on call review of patients undergoing emergency surgery

7. Outcome Measures

I. Primary outcome measure:

- Adherence to selected Enhanced Recovery After Surgery (ERAS) guidelines regarding rate of routine prophylactic drain insertion in colorectal surgery (22).

II. Secondary outcome measures:

- Rate of intra-abdominal postoperative collections, defined as collections which alter the normal postoperative course (e.g. requiring either medical, radiological, endoscopic or surgical intervention) (23).
- Time-to-diagnosis (days) of intra-abdominal postoperative collections defined as collections which alter the normal postoperative course (e.g. requiring either medical, radiological, endoscopic or surgical intervention) (23).
- Rate of drain-related complications defined as:
 - Surgical site infection (Centers for Disease Control and Prevention – CDC – definition: A surgical site infection is an infection that occurs after surgery in the part of the body where the surgery took place);
 - Cutaneous irritation at the drain insertion site (defined as reversible damage of the skin associated with rash, dry skin, itchiness, red discolouration and/or hives);
 - Small bowel evisceration and herniation of omentum (defined as prolapse of small bowel and/or omentum through the drain site after the removal of the drain);
 - Bowel injury (defined as intraoperative identification of or CT-proven drain-related iatrogenic bowel perforation) (7,24).

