Surgical site infection type	Yes - Superficial (skin or subcutaneous tissue) / Yes - Deep (fascial and muscle layers) / Yes - Organ/Space SSI (intrabdominal) / No .
Small bowel evisceration/herniation of omentum	Yes – Site of Drain(s) / Yes – Other incision / No Prolapse of small bowel and/or omentum through an incision.
Drain-related iatrogenic bowel perforation	Yes - Intraoperative / Yes – Postoperative (not during removal) / Yes – Postoperative (during removal) / No.
Drain-related skin irritation	Yes (reversible damage of the skin at the drain insertion site associated with rash, dry skin, itchiness, red discolouration and/or hives) / No
Other Drain-related complication	Please specify
Reason(s) for drain removal	
1. Clinical rationale:
 
a). Drain output satisfactory (Yes, No) - if yes: low volume, (haemo)serous fluid, other (please specify).
 
b). Drain-related complications.
 
c). Inadvertent/premature drain withdrawal.
 
d). Other (please specify)
 
2. Radiological confirmation of no significant ongoing collection (Yes - pre removal, Yes - post removal, No).

Post-operative blood transfusion	Yes / No
Day of blood transfusion	Post-operative Day (POD)
History of collection(s) requiring treatment within 30 days (either medical, surgical, endoscopic, radiological)	Yes / No
Day of collection(s) identification	Post-operative Day (POD)

Collection(s) identification method	
1. Clinical only
 
a). Symptoms. b). Change in drain output (if inserted at time of surgery).
 
2. Radiological
 
a). Imaging due to clinical suspicion b). Routine imaging as per hospital policy c). Incidental finding (imaging for other indication).

Collection(s) treatment	
Conservative management (none or antibiotic therapy) Percutaneous drainage Surgery

Total postoperative antibiotic duration	
Number of days (Total antibiotic duration including both intravenous and oral antimicrobial therapy for the treatment of the collection(s). Post-operative antimicrobial therapy started before the identification of the collection(s) should not be included.)

Outcome data points	Required data (definition / comment)
Anastomotic leak within 30 days	Yes - Radiological diagnosis / Yes - Surgical diagnosis / No
Day of anastomotic leak diagnosis	Post-operative Day (POD)
Length of hospital stay (days)	Days
30 day readmission	Yes / No

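### A collection can be counted on clinical grounds alone, and one clinical route exists only for drained patients, so the collection rate and time to diagnosis are not ascertained on the same footing with and without a drain

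*Protocol*

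**What the plan says.** Section 1 of the Methods defines the event as "Postoperative collection altering the normal postoperative course management and requiring antibiotics or radiological/endoscopic/surgical intervention". Section 7 makes two secondary outcomes of it: "Rate of intra-abdominal postoperative collections, defined as collections which alter the normal postoperative course" and "Time-to-diagnosis (days) of intra-abdominal postoperative collections defined as collections which alter the normal postoperative course". Both serve the secondary aim in section 3: "To assess whether placement of a postoperative drain is associated with earlier detection of collections and anastomotic leak".

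In Appendix A the event field is "History of collection(s) requiring treatment within 30 days (either medical, surgical, endoscopic, radiological"), answered yes or no. The identification method has two branches. The first, "Clinical only", covers symptoms or "Change in drain output (if inserted at time of surgery"). The second is radiological, and includes imaging prompted by clinical suspicion. There is no option for a collection found at reoperation or during a procedure. One postoperative day of identification is recorded, and the dictionary does not say whether this means first suspicion or confirmation. The treatment field has a conservative category that covers antibiotics or no treatment at all.

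The leak field in the same table is stricter: "Yes - Radiological diagnosis / Yes - Surgical diagnosis / No".

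**The concern.** The aim compares drained with undrained patients, but the outcome can be reached by a route that only drained patients have. Section 8 also has drain output assessed daily until removal or day 10, so that route is watched closely while a drain is in place.

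A change in output that does not reflect a true collection can add an event only to the drained group. If such events are dated earlier than genuine diagnoses, they also lower that group's average time to diagnosis. Both errors point towards the association that the aim is looking for. Section 9 plans risk adjustment for confounders, but that does not correct an outcome misclassified differently by exposure.

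**Working it through.** **Step 1: the text.** The Protocol gives no figure for this point, so the first check sets the fields side by side.

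| Item | Collection | Anastomotic leak |
|---|---|---|
| Demonstration required | No; an altered course and treatment suffice | Yes; radiological or surgical |
| Route open only to drained patients | Yes; change in drain output | None listed |
| Category for operative findings | None | Yes |
| Day recorded | Identification, undefined | Diagnosis |

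Ascertainment of collections therefore depends on exposure, and an objective standard was in use for the neighbouring outcome.

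**Step 2: possible effect on the rate.** Inputs:
- N = 5,000, the sample anticipated in section 11.
- Drained share 35%. This is an assumption; the study background gives 35% as a share of centres that routinely drain most patients, not a share of patients.
- True collection rate p = 5%, 8% or 10% in both groups (assumed).
- False output-only events in a proportion f = 0.5%, 1% or 2% of drained patients (assumed).
- Two-sided alpha 0.05 (assumed).

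Formulas: apparent risk ratio = (p + f)/p. Chance of a significant excess in the drained group = Φ[(f − 1.96·s0)/s1]. Here s0 is the pooled standard error of the difference and s1 the unpooled one.

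Worked case, p = 8% and f = 1%, with 1,750 drained and 3,250 undrained:
- Risk ratio = 0.09/0.08 = 1.125.
- Pooled rate = (3,250 × 0.08 + 1,750 × 0.09)/5,000 = 0.0835.
- s0 = √[0.0835 × 0.9165 × (1/1,750 + 1/3,250)] = 0.00820.
- s1 = √[0.08 × 0.92/3,250 + 0.09 × 0.91/1,750] = 0.00833.
- Chance = Φ[(0.01 − 1.96 × 0.00820)/0.00833] = 0.233.

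Over p = 5-10%:

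| f | Apparent risk ratio | Chance of significant excess |
|---|---|---|
| 0 | 1.00 | 2.5% |
| 0.5% | 1.05-1.10 | 8-12% |
| 1% | 1.10-1.20 | 20-33% |
| 2% | 1.20-1.40 | 59-82% |

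With 50% drained the results are similar (62-85% at f = 2%).

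**Step 3: possible effect on time.** If true collections are found on mean day d0 and false output-only events on mean day d1, the drained group's mean moves by f(d1 − d0)/(p + f). With d0 = 8 and d1 = 4 to 6 (both assumed), the mean moves earlier by 0.1-0.4 days at f = 0.5%, 0.2-0.7 days at 1% and 0.3-1.1 days at 2%. If d1 = d0 the shift is zero, so this part rests wholly on such events being dated earlier.

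**Step 4: after the change.** In an analysis limited to collections confirmed by a standard open to both groups, unconfirmed output-only events drop out and f = 0. Under equal true rates the risk ratio is then 1.00, and the shift from these events is zero.

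**The case against.** The strongest reply is that finding a collection sooner through the drain is the hypothesis itself. The background lists early detection among the reasons for draining. This stands for true collections: an earlier date obtained through drain output is then real lead time. The bias is confined to output changes that are not collections and to how they are dated. It follows that dating events only at confirmation would be a poor remedy, because it could erase genuine lead time.

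Second, a reader might infer that drained patients receive extra unconfirmed events by construction, and that clinical events are dated at suspicion. The Protocol supports neither. It makes such events possible but gives no frequency, and it leaves the day of identification undefined. An output change that leads to a scan can be coded as radiological. A collection identified clinically may later be proven by surgery or percutaneous drainage, so the clinical category is not the same as unconfirmed.

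Third, the event must alter the course and be treated, which limits spurious entries. This stands in part: antibiotics are enough, and the treatment field's no-treatment option contradicts the event field.

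Fourth, the form records identification method, treatment and daily drain contents, so a sensitivity analysis could be left to the statistical analysis plan. This also stands only in part. With no operative category, a collection proven at reoperation without imaging has no place except the clinical branch, beside unconfirmed ones. With one undefined day, the date of confirmation cannot be recovered later.

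Finally, accepting clinical diagnoses is a defensible choice in an audit of routine care, and a strict leak field does not oblige the collection field to match it. That lowers the weight of the point but does not make the two groups comparable.

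**Conclusion.** The point holds in a limited form. The collection outcome can be met on clinical grounds alone, and one clinical route is closed to undrained patients. False events through that route can only raise the drained group's rate, and they shorten its time to diagnosis if they are dated earlier. The Protocol does not show that this will happen or how often. The risk ratios of 1.05-1.40 and shifts of 0.1-1.1 days rest on assumed event rates, assumed dates and an assumed drained share; they show scale and are not predictions.

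Two secondary outcomes serving a stated secondary aim are affected. The primary outcome, adherence on drain insertion, is not. The change is worth making in the Protocol and data dictionary before data collection, because a confirmed-only comparison cannot be fully rebuilt from the fields as they stand.

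**What to change.** In Appendix A:
- Add an operative or procedural option to the collection identification method.
- Add a yes/no field for confirmation by imaging, operation or aspirate.
- Replace the single day by the day of first identification and the day of confirmation.
- Reconcile the event field, which presupposes treatment, with the treatment category that allows none.

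In section 7, state that the comparison of drained with undrained patients on collection rate and time to diagnosis will be reported in two ways: for collections confirmed by a standard available to both groups (imaging, operation or aspirate), and for all treated collections. Show events identified by drain output alone separately. This should include purulent or faecal output, since accepting drain fluid as confirmation would keep a drained-only route. Report time to first identification and time to confirmation, so that real lead time stays visible.

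The cost is two or three extra form fields, some wording in section 7, and fewer events in the confirmed-only analysis.

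### The collection treatment field pools no treatment with antibiotics and omits endoscopy, so untreated collections can be recorded as cases and cannot be reliably picked out later

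*Protocol*

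**What the plan says.** Methods section 1 defines the event: "Postoperative collection altering the normal postoperative course management and requiring antibiotics or radiological/endoscopic/surgical intervention". Treatment is part of the definition.

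Section 7 lists two secondary outcomes built on it. The first is "Rate of intra-abdominal postoperative collections, defined as collections which alter the normal postoperative course (e.g. requiring either medical, radiological, endoscopic or surgical intervention". The second is "Time-to-diagnosis (days) of intra-abdominal postoperative collections defined as collections which alter the normal postoperative course", followed by the same bracketed example. In both, the criterion is an altered postoperative course, and treatment only illustrates it.

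Appendix A has a Yes/No item, "History of collection(s) requiring treatment within 30 days (either medical, surgical, endoscopic, radiological", followed by the day and method of identification. The treatment field then has three options: "Conservative management (none or antibiotic therapy", percutaneous drainage, and surgery. A further field records total days of antibiotics for the collection, with this limit: "Post-operative antimicrobial therapy started before the identification of the collection(s) should not be included".

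Section 3 makes the incidence of complicated collections and the way they were managed a secondary aim.

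**The concern.** A collection that meets the section 1 definition, or that earns a Yes on the Appendix A item, cannot have had no treatment. Yet *none* is a printed answer in the treatment field, so a data collector may reasonably conclude that an untreated collection belongs in the record. Because *none* shares a code with antibiotics, such a record does not show itself afterwards. The collection rate and the time to diagnosis both depend on which collections count, and the time to diagnosis serves the aim on whether drains bring earlier detection.

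Endoscopic treatment is a second and separate gap. The definition, both outcomes and the Yes/No item name it, but the treatment field has no place for it.

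**Working it through.** No arithmetic applies: the protocol gives no expected collection rate, no share of collections left untreated and no power figure for these outcomes. The check is a comparison of the texts, then of what the recorded fields can recover.

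**Step 1. The texts side by side**

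| Place | Must treatment have been needed? | Endoscopic treatment named? |
|---|---|---|
| Section 1, definition | Yes | Yes |
| Section 7, rate and time to diagnosis | Not strictly; given as an example | Yes |
| Appendix A, Yes/No item | Yes | Yes |
| Appendix A, treatment field | No; *none* is accepted | No |

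A data collector therefore meets three positions: treatment required, treatment as an example, and no treatment accepted. The protocol does not say what happens to a record that answers Yes and then has no treatment.

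**Step 2. Can untreated cases be found later?** Take a record with Yes and the conservative code.

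- *Antibiotic days above 0.* The collection was treated with antibiotics. Resolved.
- *Antibiotic days equal to 0.* Either nothing was given, or all the antibiotics began before the collection was identified and so are not counted. Not resolved by this field.
- *Antibiotic days equal to 0, highest Clavien-Dindo grade None or I.* Appendix C puts antibiotics for a complication at grade II or above, so this pattern indicates no antibiotic treatment. Resolved, if the grade was assigned correctly.
- *Antibiotic days equal to 0, highest grade II or above.* Only the highest grade is kept, and it may come from another complication. Not resolved.

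So one group stays ambiguous: conservative code, zero counted days, grade II or above. The method of identification does not settle it, because a collection found by routine or incidental imaging may or may not have been treated.

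**Step 3. Endoscopic treatment.** Such a collection is correctly Yes on the case item, and its day of identification is recorded, so the rate and the time to diagnosis are intact. At the treatment field the collector must choose a wrong option or leave it blank. A blank counts towards the missing data for which section 14 excludes centres above 5%. The loss falls on the section 3 aim about management.

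**The case against.** The strongest reply is that the Yes/No item, not the treatment field, matches the two outcomes. Completed as worded, it gives No for an untreated collection, which then enters neither the rate nor the timing. The treatment field is a later descriptor, and nothing says that it defines an outcome. This stands, and it limits the point to what can happen when a collector takes *none* at face value.

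Second, the pooled cases are partly separable through antibiotic days and Clavien-Dindo grade. This also stands, apart from the ambiguous group in the working.

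Third, only the dictionary is visible. The REDCap form may have branching or checks that are not shown, and the handling of a Yes record with no treatment could sit in the analysis plan. That is fair for the handling rule. An analysis plan cannot, however, restore a distinction that was not captured.

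A reader might go further and infer that untreated collections do enter both outcomes, that routine imaging inflates the rate at centres that scan by policy, or that imaging around drain removal makes the error differ by drain status. The documents do not support these readings. Appendix A lists routine imaging as a route of identification but does not make every finding a case, it records that route so that such cases can be examined, and no frequency of such imaging is given.

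**Conclusion.** The inconsistency is certain; its effect on the outcomes is possible and of unknown size. Untreated collections can be recorded as cases, and some could not then be told apart from antibiotic-treated ones. Any percentage for the overstatement would rest on an assumed collection rate and an assumed untreated share, so none is offered. That untreated cases get in at all rests on the assumption that some collectors will read *none* as permission to answer Yes.

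Two consequences need no such assumption. An endoscopically treated collection has no correct option in the dictionary, and the treatment code itself cannot separate antibiotics from no treatment. Both weaken the description of clinical management. The primary outcome, adherence on drain insertion, is untouched. The change is worth making but is not critical.

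**What to change.** 1. Use one collection definition in section 1, section 7 and Appendix A. In section 7, state the treatment requirement as a condition, not as an example. Settle at the same time whether *medical* (section 7 and Appendix A) means the same as *antibiotics* (section 1).
2. Replace the three treatment options with five: none; antibiotics only (including those continued or changed); percutaneous drainage; endoscopic; surgery.
3. State that the rate and the time to diagnosis count only records with Yes on the collection item and a treatment other than none.

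The cost is two extra form options (5 - 3 = 2) and aligned wording. It changes what is recorded, not how patients are managed. It is cheap before data collection and hard afterwards: section 12 has paper copies destroyed after upload and makes the local list linking records to hospital numbers optional.

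### The antibiotic-duration field in Appendix A excludes therapy by its start date, so a course begun on suspicion and continued as treatment of the collection has no clear day count

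*Protocol*

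**What the plan says.** The field is in the drain-related part of Appendix A (Data Dictionary), among the items on collections. It is recorded as a number of days and has two sentences of definition. The first sets the scope: "Total antibiotic duration including both intravenous and oral antimicrobial therapy for the treatment of the collection(s)". The second is an exclusion: "Post-operative antimicrobial therapy started before the identification of the collection(s) should not be included".

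Three neighbouring items matter. The date item is "Day of collection(s) identification", a single postoperative day. The identification-method item includes "Imaging due to clinical suspicion" among its radiological options. The treatment item has a category "Conservative management (none or antibiotic therapy)", alongside percutaneous drainage and surgery.

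The field serves the secondary aim in section 3: "To characterise the incidence of complicated postoperative collections and their clinical management in colorectal surgery in an international cohort". Antibiotic duration is not listed among the primary or secondary outcome measures in section 7.

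**The concern.** The two sentences sort the same course differently. Antibiotics started on suspicion and then continued because a collection was found are, from identification onward, treatment of that collection, so the first sentence takes them in. The second takes them out, because the therapy began earlier. It removes the therapy as a whole, not just the days before identification, and makes no exception for a course that carries on as treatment.

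Collectors then have two defensible ways to fill the box. Some will follow the wording and enter no days; others will count from identification. Section 11 anticipates 150 + 150 = 300 centres, and section 14 has medical students leading delivery alongside junior doctors, so both readings are likely to occur. A summary of antibiotic days would then mix two definitions, and wherever the literal one is used it would be too short as a measure of treatment given.

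**Working it through.** The protocol gives no figure for this field, so there is nothing to reproduce. The check applies the written rule to a course and asks whether other items could repair the result.

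**Step 1: three ways to count.** Let s be the postoperative day on which antibiotics start, d the day of identification and e the last day of the same unchanged course, with s < d.

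- Rule as written: 0, because the therapy started before d.
- Days from identification only: e − d + 1.
- Whole course: e − s + 1.

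**Step 2: an example.** The days are assumed for illustration and are not in the protocol: s = 4, d = 6, e = 12.

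- Rule as written: 0 days.
- From identification: 12 − 6 + 1 = 7 days.
- Whole course: 12 − 4 + 1 = 9 days.

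Keep s = 4 and e = 12 and move identification from day 5 to day 8. The count from identification falls from 12 − 5 + 1 = 8 to 12 − 8 + 1 = 5. The rule as written stays at 0 throughout.

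**Step 3: when the problem arises.** It needs a course that started before identification and continued unchanged. A new or changed course started at or after identification is counted. So is a course started on the day a collection is identified clinically, since it did not start before identification. The problem case is still one that the form foresees: imaging prompted by clinical suspicion leaves an interval in which antibiotics may already be running.

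**Step 4: can analysis repair it?** Section 9 points to Appendix A and the database for the full list of required fields. Appendix A has the day of identification but no day on which antibiotics started, so an analyst cannot find the affected courses or recompute them under one rule. The treatment item does not help. Its conservative category combines no treatment with antibiotic therapy, so a zero produced by the rule looks the same as a true zero.

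**Step 5: size.** Suppose the intended quantity is days from identification. The average shortfall across collections is then (share with antibiotics already running and continued unchanged) × (share of those recorded literally) × (mean days from identification in those courses). The protocol supplies none of the three factors, so no estimate follows from it.

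**The case against.** The best defence is that the second sentence was probably meant to keep out earlier post-operative antibiotics given for other reasons. Such courses are foreseeable, because the study includes emergency, perforated, contaminated and dirty cases. Read with the first sentence, a sensible collector would count from identification. The case report form and the e-learning modules, which are not available here, may say so. The likely intent is accepted. But the first sentence already limits the count to therapy for the collection, which largely serves that purpose, and counting a running course from identification needs words that the second sentence lacks.

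Two stronger readings are tempting, and the protocol does not support them.

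- A reader might infer a contradiction with section 1 of the Methods, where a collection counts if it is one "requiring antibiotics or radiological/endoscopic/surgical intervention": a collection could qualify through antibiotics and still carry zero antibiotic days. That would look odd in the data but is not a contradiction. Whether a patient had a qualifying collection is a separate yes/no item that does not depend on the duration field. Incidence, day of identification and treatment category are untouched.
- A reader might infer a bias by drain status, since a change in drain output is an identification route open only to drained patients, and earlier identification would leave fewer courses already running. That mechanism is possible. However, the aim on drains in section 3 concerns earlier detection of collections and leak, and the protocol specifies no comparison of antibiotic days by drain status.

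It is also fair to say that whether to count the whole course, the days from identification or only new therapy is a choice of definition. The objection is not to any one of these choices. It is that the present wording does not settle a foreseeable case in line with the field's stated purpose.

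**Conclusion.** The point holds as a minor defect in a data definition. Taken literally, the exclusion gives no days for a course that began on suspicion and continued unchanged as treatment. Taken as probably intended, it gives the days from identification. The protocol does not say which applies, and the items collected do not allow the two to be separated afterwards.

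The consequence is limited to the description of antibiotic duration under the management aim. The primary outcome, every secondary outcome in section 7 and the anticipated sample are unaffected. It would go too far to say that continued courses will all be recorded as zero, or that the reported mean or median will be wrong by a stated amount. Either claim requires every collector to read the rule literally and requires figures for pre-identification treatment that the protocol does not give. The 0, 7 and 9 days above illustrate the rule and do not estimate the error.

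**What to change.** Replace the second sentence of the field with a rule that counts days, for example: *Count days of antimicrobial therapy for the collection(s) from the day of identification onward, including therapy that began earlier and was continued as treatment; do not count days before identification or therapy given for another reason.*

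This keeps the probable purpose of the present sentence and removes the conflict with the first. It uses the identification day already collected, needs no new item, and concerns only how days are counted, not how antibiotics are given. The cost is one sentence in the data dictionary, with the same wording carried into the case report form and training material. The small downside is that empirical days before identification stay uncounted, as they do under the present rule.
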